**\*\*\* Subject Population \*\*\***

**Subject Population(s) Checklist**

**Select All That Apply :**

- X Adults
- Cognitively Impaired Subjects
- Employees (specifically targeted)
- Fetuses
- Minors (under 18)
- Neonates
- Non English Speaking Subjects
- Pregnant Women
- Prisoners
- Students (specifically targeted)
- Terminally Ill Subjects
- Wards of the State
- Other (any population that is not specified above)

---

**\*\*\* Study Location \*\*\***

**Study Location(s) Checklist**

**Protocol Title:** Analysis of hemostatic agents compared to physiologic hemostasis

---

**General Checklist**

**Select All That Apply :**

- Collection of Specimens  
 Data collection via e-mail or the Internet  
 Deception/Incomplete Disclosure  
 Dietary Supplements, Vitamins, and Other Food Agents
- X FDA Approved Device  
 FDA approved drugs, reagents, other chemicals administered to subjects (even if they are not being studied), or biologic products  
 Genetic Testing  
 HIV Testing  
 Human blood, cells, tissues, or body fluids  
 International Research or Research on International Populations  
 Investigational drugs, reagents, chemicals, or biologic products  
 Investigational Device
- X Investigator Initiated Study    \*?HELP?\*
- X Medical Records  
 Photography, Video, or Voice-Recording Subjects
- X Questionnaires and/or tests  
 Radioisotopes/radiation-producing machines, even if standard of care  
 rDNA/Gene Transfer Therapy  
 Registry(ies)  
 Specimens to be stored for future research projects (must be in consent form)  
 Study of existing data or specimens

**Protocol Title:** Analysis of hemostatic agents compared to physiologic hemostasis

---

- X University Indemnified Study (SLU is responsible for liability coverage) **\*?HELP?\***  
Other (clarify in text box to the right)

Single Use. Provide a brief summary and justification for the Single Use Therapy. Note: This application will refer to research. For Single Use applications it is understood that 'research' will mean 'therapy'.

---

**\*\*\* Funding \*\*\***

**Funding Checklist**

- X NONE

**Funding - Grants/Contracts**

**Funding - Industry Sponsor**

**NOTE: Applicable grant application, contract or subcontract, investigator's brochure, and sponsor's protocol (for all industry sponsored clinical trials) must be attached. You will be prompted for these in section #16 (Attachments).**

---

**\*\*\* Expedited Paragraphs \*\*\***

To request an Expedited Review, check the appropriate category(ies) below. Provide justification for your request for Expedited Review.

To qualify for expedited review, research activities must (1) present no more than minimal risk to human subjects, and (2) involve only procedures listed in one or more of the categories below.

1. Clinical studies of drugs and medical devices only when condition (a) or (b) is met.
  - a) Research on drugs for which an investigational new drug application (21 CFR Part 31, 32) is not required. (Note: Research on marketed drugs that significantly increases the risks or decreases the acceptability of the risks associated with the use of the product is not eligible for expedited review.)

**Protocol Title:** Analysis of hemostatic agents compared to physiologic hemostasis

---

- b) Research on medical devices for which
  - (i) An investigational device exemption application (21 CFR Part 812) is not required; or
  - (ii) The medical device is cleared/approved for marketing and the medical device is being used in accordance with its cleared/approved labeling.

2. Collection of blood samples by finger stick, heel stick, ear stick, or venipuncture as follows:

- a) From healthy, nonpregnant adults who weigh at least 110 pounds. For these subjects, the amounts drawn may not exceed 550 ml in an 8-week period and collection may not occur more frequently than 2 times per week; or

From other adults and children, considering the age, weight, and health of the subjects, the collection procedure, the amount of blood to be collected, and the frequency with which it will be collected. For these subjects, the amount drawn may not exceed the lesser of 50 ml or 3 ml per kg in an 8-week period and collection may not occur more frequently than 2 times per week.

Children are "persons who have not attained the legal age for consent to treatments or procedures involved in the research, under the applicable law of the jurisdiction in which the research will be conducted."

3. Prospective collection of biological specimens for research purposes by non-invasive means.

**EXAMPLES:** (a) hair and nail clippings in a nondisfiguring manner; (b) deciduous teeth at time of exfoliation or if routine patient care indicates a need for extraction; (c) permanent teeth if routine patient care indicates a need for extraction; (d) excreta and external secretions (including sweat); (e) uncannulated saliva collected either in an unstimulated fashion or stimulated by chewing gumbase or wax or by applying a dilute citric solution to the tongue; (f) placenta removed at delivery; (g) amniotic fluid obtained at the time of rupture of the membrane prior to or during labor; (h) supra- and subgingival dental plaque and calculus, provided the collection procedure is not more invasive than routine prophylactic scaling of the teeth and the process is accomplished in accordance with accepted prophylactic techniques; (i) mucosal and skin cells collected by buccal scraping or swab, skin swab, or mouth washings; (j) sputum collected after saline mist nebulization.

4. Collection of data through non-invasive procedures (not involving general anesthesia or sedation) routinely employed in clinical practice, excluding procedures involving X-rays or microwaves. Where medical devices are employed, they must be cleared/approved for marketing. (Studies intended to evaluate the safety and effectiveness of the medical device are not generally eligible for expedited review, including studies of cleared medical devices for new indications.)

**EXAMPLES:** (a) physical sensors that are applied either to the surface of the body or at a distance and do not involve input of significant amounts of energy into the subject or an invasion of the subjects' privacy; (b) weighing or testing sensory acuity; (c) magnetic resonance imaging; (d) electrocardiography, electroencephalography, thermography, detection of naturally occurring radioactivity, electroretinography, ultrasound, diagnostic infrared imaging, doppler blood flow, and echocardiology; (e) moderate exercise, muscular strength testing, body composition assessment, and flexibility testing where appropriate given the age, weight and health of the individual.

**Protocol Title:** Analysis of hemostatic agents compared to physiologic hemostasis

---

5. Research involving materials (data, documents, records, or specimens) that have been collected, or will be collected solely for nonresearch purposes (such as medical treatment or diagnosis). (NOTE: Some research in this category may be exempt from the HHS regulations for the protection of human subjects. 45CFR 46.101(b)(4). This listing refers only to research that is not exempt.)
6. Collection of data from voice, video, digital, or image recordings made for research purposes.
7. Research on individual or group characteristics or behavior (including, but not limited to, research on perception, cognition, motivation, identity, language, communication, cultural beliefs or practices, and social behavior) or research employing survey, interview, oral history, focus group, program evaluation, human factors evaluation, or quality assurance methodologies. (NOTE: Some research in this category may be exempt from the HHS regulations for the protection of human subjects. 45 CFR 46.101(b)(2) and (b)(3). This listing refers only to research that is not exempt.)
- X 8. [FOR IRB use only]. Continuing review of research previously approved by a convened IRB only when condition (a), (b), or (c) is met.
  - a) Previously approved research where
    - (i) The research is permanently closed to the enrollment of new subjects;
    - (ii) All subjects have completed all research-related interventions; and
    - (iii) The research remains active only for the long term follow-up of subjects.
  - b) Previously approved research where no subjects have been enrolled and no additional risks have been identified.
  - X c) Previously approved research where the remaining research activities are limited to data analysis.
9. [FOR IRB use only]. Continuing review or research not conducted under an investigational new drug application or investigational drug exemption where expedited categories two (2) through eight (8) do not apply but the IRB has determined and documented at a convened meeting that the research involves no greater than minimal risk and no additional risks have been identified.

---

**\*\*\* Background, Purpose, Study Procedures \*\*\***

**Title**

Analysis of hemostatic agents compared to physiologic hemostasis

Complete Sections 1 - 16. In sections that allow reference to sponsor protocol or grant, clearly state section and page numbers. Any information that is different or specific to the local site should be in the SLU application. Specify N/A as appropriate.

**1. Background**

**Protocol Title:** Analysis of hemostatic agents compared to physiologic hemostasis

---

Page numbers from a sponsor's protocol/grant may be referenced in 1a and 1b.

- a) **Provide an introduction and background information. Describe past experimental and/or clinical findings leading to the formulation of the study, if applicable. Investigator Initiated studies must cite references in the response provided or attach a bibliography. *\*?HELP?\****

In this study we wish to determine if the use of hemostatic agents after endoscopic sinus surgery is superior to no agent at all. We will treat patients with one of many different FDA approved hemostatic agents in one of their nostrils and compare it to a side in which no therapy is applied. We will then evaluate qualities of the patient's recovery (synechia formation, granulation, edema, infection, and time spent debriding the sinuses) in response to intervention.

Functional endoscopic sinus surgery (ESS) is a safe, commonly performed procedure primarily in an outpatient setting. One of the most prevalent complications is post-operative epistaxis. To prevent this nasal packing is often employed. Traditionally non-absorbable packing was employed; yet, this has fallen out of favor with most otolaryngologists considering the great discomfort of the packing, especially upon removal (von Schoenberg). In addition to this, with removal of non-absorbable packing interruption of the wound bed is inevitable. This has led to a paradigm shift towards absorbable packing, which are biomaterials that provide substrate to stimulate clotting. Absorbable hemostatic agents tend to spare the mucosa and are less painful upon removal (Maccabee). However, absorbable packing comes with the possible drawback of increased rates of synechia formation secondary to initiation of local inflammation (Valentine). Standard of care is no packing, one of these types of absorbable packing, or removing packing.

a). Sinufoam is a carboxymethylcellulose (CMC) derivative which provides a moist wound environment and with its viscosity and density, provides a scaffold for epithelialization and pressure lateralization against surfaces to which it is applied (Al-Reefy). On the other hand, Arista is composed of potato-starch derived mucopolysaccharide hemospheres (MPH) which are rapidly cleared from the human body with minimal interruption in wound healing ([name]). Nexfoam is made from plant pectin and is also rapidly cleared from the nasal cavity.

b). AristaTM is FDA approved for endonasal use and is currently available on the market. NexfoamTM is FDA approved for use as a topical dressing for the temporary treatment of moderate to severely bleeding wounds such as surgical wounds (post operative, donor sites, dermatological) and it has the number: K070211 under the name of TraumArrestTM. It also falls under Class I medical device that is exempt from the premarket notification procedures. SinufoamTM (Stamberger) is included under Rapid Rhino product line (RR 650) and it is a Class I medical device, FDA product registration is attached.

c). Nasopore nasal dressing is a fragment-able nasal dressing and is indicated for use in patients undergoing nasal/sinus surgery as a space occupying stent to separate and prevent adhesions between mucosal surfaces; to help control minimal bleeding following surgery or nasal trauma by tamponade effect and blood absorption. It is FDA approved and filed under number K052099.

d). Nexfoam is a sterile, topical wound dressing comprised of plant based polysaccharides. The hemostatic particles dehydrate blood cells, resulting in hemoconcentration of platelets, serum proteins and fibrinogen, leading to clotting that limits and controls bleeding. It is FDA approved and filed under number K122886.

e). The Hemostasis PosiSep and PosiSep X Hemostat Dressings are sterile hemostats comprised of modified Chitosan particles and polysaccharide binders. Chitosan has well known hemostasis

properties and, when combined with carboxymethylcellulose and hydroxyethylcellulose binders,

forms a foam-type dressing that has an affinity to absorb and hold water. The PosiSep and PosiSep X Hemostat Dressings are used for topical wounds. The dressings quickly dehydrate blood cells, thereby

causing rapid hemoconcentration of platelets, serum proteins and fibrinogen, leading to clotting that limits and controls bleeding and edema. It is FDA approved and filed under K120958.

f). Sinufoam, Arista, Nasopore, Nexfoam, Posisep and PosiSep X are all being used for purposes approved following sinus surgery by the FDA.

**Protocol Title:** Analysis of hemostatic agents compared to physiologic hemostasis

---

purposes approved following sinus surgery by the FDA.

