**Please save frequently**

- c) Describe the study design (e.g., single/double blind, parallel, crossover, control, experimental, observational, etc.). If the study is investigator-initiated, a timeline for individual subject recruitment, follow-up, and analysis for the study is required. Also, indicate if the subjects will be randomized.

Our study is a prospective comparison between absorbable hemostatic agents as a group and the body's natural hemostatic ability without aid of therapy in patients undergoing bilateral sinus surgery with or without septoplasty.

We calculated the sample size and power analysis in the following way:

Given the number of statistical tests, we calculated a Bonferonni correction to set the alpha for the analysis at 0.017 (alpha originally at .05 divided by the number of tests = .05/30 = 0.017). Using G-Power statistical software, power analyses were completed using the Means: Wilcoxon-Mann-Whitney test (two groups). Given alpha at 0.017 and Power at 0.80, we determined that a total of 244 participants (122 in the control group, 122 in the hemostatics group) would be needed to detect a medium effect size (d=0.5). Since one nostril will be used as the control and the therapy applied to the other side, the number of participants needed drops to 122.

Based on previous studies, we conservatively expect a dropout rate of 15%. In order to maintain the same number of participants, we would need to enroll a total of 144 participants

Postoperatively, patients will rate subjective symptoms such as nasal obstruction, bleeding,

**Protocol Title:** Analysis of hemostatic agents compared to physiologic hemostasis

---

pain, and nasal discharge on a scale ranging from 1-10, of which 10 is the most severe. Similarly, the treating physicians on endoscopic examinations will rate objective measures such as mucosal edema, infection, time spent debriding, and synechiae formation. (Please see the attached patient and physician questionnaires) Patient questionnaires will be completed on postoperative days #1, 2, 7, and 14. Surgical healing outcomes will be noted during routine postoperative visits 1 and 2 weeks after surgery. Expected total duration of each subjects' participation is 6 weeks. Total subject accrual should take no longer than one year. Data analysis will take up to three months. Estimated time of completion is 03/2018.

d) **If subjects will be given placebo, please justify placebo use. \*?HELP?\***

N/A

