**If No, explain what SLU will NOT participate in:**

**Please save frequently**

Page numbers from a sponsor's protocol/grant may be referenced in 3b, 3c, and 3d.

- b) **Describe all the procedures, from screening through end-of-study, that the human subject must undergo in the research project, including study visits, drug treatments, randomization and the procedures that are part of standard of care. Specify which procedures are for research and which are standard of care. Please note: The box below is for text only. If you would like to add tables, charts, etc., attach those files in the Attachment section (#16).**

a.) Patients will have (standard of care) Endoscopic Sinus Surgery.  
 b.) Each patient will receive a hemostatic agent in one nostril and nothing in the other nostril.  
 c.) Products will be placed in patients' post-operative sinus cavities at the end of the procedure according to company recommended instructions. Essentially all products placed in the middle meatus are allowed to remain there until absorbed or removed at a post operative visit on weeks 1, 2, and 6. Post-operative irrigations (Standard of Care) will remove much of the material. Any residual material is removed in the office on normal, (Standard of Care) post-operative debridement on weeks 1, 2, and/or 6.  
 d.) Subjects will provide subjective pre- and post-operative data, such as rating their pain, bleeding, obstruction, and discharge on days 0, 1, 2, 7, and 14 (Standard of Care).  
 e.) Patients will be given a questionnaire packet pre-operatively (Research Related). Questionnaires will include post-operative data on days 0, 1, 2, 7, and 14. They are asked to bring completed questionnaires on standard post-operative visits.  
 f.) The physician will record objective and subjective data (synechiae, edema, infection, granulations, and time spent debriding) upon regular reexamination of the sinuses after surgery, at post-operative visits on weeks 1, 3, and 6. All procedures are standard clinical care.  
 g.) Follow up visits will conform to standard clinical care; patients will be seen in the physician's clinic.

**Protocol Title:** Analysis of hemostatic agents compared to physiologic hemostasis

---

clinic.

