- c) If the proposed study is a clinical trial where a drug, vaccine, device or other treatment is compared to a placebo group or comparison treatment group, what are the guidelines or endpoints by which early decisions regarding efficacy or lack of efficacy can be made? For example, it may be reasonable to stop enrollment on a study when efficacy has already been clearly demonstrated, to avoid unnecessary enrollments of additional subjects. Alternatively, it may be reasonable to stop enrollment when it is clear that efficacy will never be demonstrated, given the statistical power of the study as designed. Describe the guidelines that are in place to assist in making these determinations, if relevant to the proposed study.

If side effects or discomforts do occur, [name] and/or [name] will try to minimize and treat these by irrigating the treated sinus with saline to remove the Arista, Nexfoam, Sinufoam, Nasopore, Posiseq, or Posiseq X.

- d) Describe how data analysis will be performed (statistical tests, methods of evaluating data) and indicate the smallest group/unit for which separate reporting will occur. For studies involving a questionnaire, if data and reliability information are available, please describe or provide references. For full board, unfunded studies describe sample size determination and power analysis. If none, please justify.

Means and standard deviations will be obtained for data collected from patients and the physician. These outcomes will be used for comparative evaluation of hemostatic agents (n=144) against no therapy. Statistics will include descriptive statistics and a non-parametric ANOVA comparing the questionnaire patient data and the physician data followed by Post-hoc multiple comparisons.

Please save frequently

- e) State if deception (including incomplete disclosure of study purpose/procedures) will be used. If so, describe the nature of the deception and provide a rationale for its use. Also, describe debriefing procedures or justify a waiver of the requirement to debrief. NOTE: for studies using deception, an alteration of consent must be justified in the Informed Consent section of the protocol (#13) and the debriefing script/statement must be uploaded in the Attachments section (#16). See IRB Deception Guidelines.

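### Synechiae, named in the plan as a possible harm of absorbable packing, has no paired frequency or confidence interval and no exemption from the 30-test alpha

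*Combined protocol and SAP*

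**What the plan says.** Section 1 a) asks whether to "determine if the use of hemostatic agents after endoscopic sinus surgery is superior to no agent at all". The recovery outcomes it lists are "synechia formation, granulation, edema, infection, and time spent debriding the sinuses". The same section states the possible harm: "absorbable packing comes with the possible drawback of increased rates of synechia formation secondary to initiation of local inflammation".

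Section 2 c) sets the significance level: "Given the number of statistical tests, we calculated a Bonferonni correction to set the alpha for the analysis". The arithmetic is printed as "alpha originally at .05 divided by the number of tests = .05/30 = 0.017". The 30 tests are not listed and no outcome is exempted. The sample size there uses a two-group Wilcoxon-Mann-Whitney test with d = 0.5 and power 0.80. It gives 122 per group, taken as 122 patients because each is their own control, and 144 after 15% dropout. Sidedness is not stated.

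Section 3 d) contains the analysis: "Means and standard deviations will be obtained for data collected from patients and the physician", then a non-parametric ANOVA and post-hoc comparisons. It has no separate safety analysis, no paired table and no confidence interval.

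Section 3 b) has the physician record synechiae and infection after surgery. Section 9 lists infection among the risks but not synechiae, and says there is no data safety monitoring plan. Section 10 expects the findings to inform physicians about effects and side effects.

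**The concern.** A Bonferroni correction guards against false claims across many tests. For a benefit claim, that is its purpose. For a harm foreseen in the background section, the same correction raises the bar for saying that the harm occurred, and nothing else in the plan makes up for it. The possible harm is described as a rate, but a rate compared between the two sides of the same patient is not among the planned outputs. Nor is an interval that would show how large an excess the data leave open.

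At stake is how a non-significant synechiae result can be read. Without the paired counts and an upper confidence limit, a reader cannot tell evidence against an increase from too little information.

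**Working it through.** **1. The plan's own sample size.** For the Wilcoxon-Mann-Whitney test by asymptotic relative efficiency, effective n = n × 3/π, noncentrality = d × √(effective n / 2) and df = 2 × effective n − 2. With n = 122 and d = 0.5, effective n = 116.5 and noncentrality = 0.5 × √58.25 = 3.82. Smallest n per group for power 0.80:

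| Alpha | One-sided | Two-sided |
|---|---|---|
| 0.05/30 = 0.00167 | 122 (power 0.801) | 136 |
| 0.017 as printed | 75 | 89 |

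The plan's 122 appears only at 0.05/30, one-sided. The printed 0.017 is 0.05/3, ten times larger. Dropout: 122/0.85 = 143.5, so 144, as stated. Because the two alphas conflict, both are carried forward.

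**2. Assumptions.** The documents give no synechiae rate, so untreated rates p0 of 5% to 20%, doubled on the treated side (p1), are assumed. Synechiae is taken as yes/no. The between-side correlation φ is set at 0, 0.3 and 0.5; section 8 h) requires similar disease on both sides, so 0 is pessimistic. There are 122 evaluable pairs.

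**3. Paired probabilities.** Both sides: p11 = p0·p1 + φ√[p0(1−p0)p1(1−p1)]. Treated only: b = p1 − p11. Untreated only: c = p0 − p11. For 10% v 20% the square root is √(0.10 × 0.90 × 0.20 × 0.80) = 0.12:

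| φ | p11 | b | c |
|---|---|---|---|
| 0 | 0.020 | 0.180 | 0.080 |
| 0.3 | 0.056 | 0.144 | 0.044 |
| 0.5 | 0.080 | 0.120 | 0.020 |

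**4. Chance of flagging the excess.** Discordant pairs M ~ Binomial(122, b + c). Given M, treated-only events ~ Binomial(M, b/(b + c)). The excess is flagged if the two-sided exact McNemar p-value is at or below alpha with more events on the treated side. Summed over M, for φ = 0 / 0.3 / 0.5:

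| Untreated v treated | 0.05/30 | 0.017 | 0.05 |
|---|---|---|---|
| 5% v 10% | 2.5 / 3.3 / 4.1% | 12 / 17 / 25% | 24 / 31 / 41% |
| 10% v 20% | 13 / 23 / 37% | 36 / 51 / 69% | 52 / 68 / 84% |
| 15% v 30% | 31 / 52 / 77% | 61 / 80 / 94% | 77 / 89 / 98% |
| 20% v 40% | 55 / 79 / 96% | 82 / 95 / 99% | 91 / 98 / 99.8% |

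The chance for a doubling first reaches 50% at an untreated rate of about 20 / 15 / 12% (0.05/30), 13 / 10 / 8% (0.017) or 10 / 8 / 6% (0.05).

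**5. What an interval would add.** The 95% half-width for the paired risk difference is 1.96 × √{[b + c − (b − c)²]/122}. For 10% v 20%:

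- φ = 0: 1.96 × √(0.250/122) = 8.9 points
- φ = 0.3: 1.96 × √(0.178/122) = 7.5 points
- φ = 0.5: 1.96 × √(0.130/122) = 6.4 points

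Around an observed excess of 10 points, the upper limit would be about 16 to 19 points. That is the figure a reader needs beside a non-significant p-value.

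**The case against.** Synechiae is a legitimate outcome in either direction. The background calls the increase only possible, section 1 describes one study agent (Nasopore) as indicated to prevent adhesions, and section 9 says earlier data conflict. Placing it in the efficacy family is therefore defensible. This stands, and it is why a claim of reduction should stay in that family.

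The yes/no model may also be wrong. Section 2 c) says physicians will rate these measures, which could mean grades. For a graded score at the plan's d = 0.5, a paired signed-rank test with 122 pairs (efficiency 3/π, two-sided, correlation 0 to 0.3) has 72-91% power at 0.05/30 and 92-98% at 0.017. This stands too: the percentages in the table are conditional on a binary item.

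Four stronger readings are tempting, and the documents do not support them:

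- A reader might infer that a doubling would most likely be missed. That holds only below the untreated rates given above, and no rate is documented.
- A reader might infer from the sample size that the analysis is one-sided and so cannot show harm at all. Sidedness is stated nowhere, and the planned ANOVA is non-directional. A possible setting in the sizing software is not an analysis rule.
- A reader might infer that a non-significant result will be reported as no difference. No reporting rule is given. Descriptive statistics are planned, and the mean of a 0/1 item is its rate, so 20% beside 10% would be visible.
- A reader might infer that an unadjusted interval would always reveal the excess. At 0.05 the 10% v 20% case is detected 52-84% of the time, so the interval would often include zero.

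**Conclusion.** The point holds in conditional form. A possible harm named in the background is put under an alpha corrected for 30 tests, without exemption, and is given no paired frequency and no confidence interval. That is plain from sections 1 a), 2 c) and 3 d) and needs no assumed rate.

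Its size does need assumptions. In the 10% v 20% case, moving from 0.05 to 0.05/30 cuts the chance of flagging the excess from 52-84% to 13-37%; at the printed 0.017 it is 36-69%. These figures rest on a binary item, 122 pairs, a two-sided exact McNemar test and correlation 0 to 0.5. At untreated rates near 20% the loss is much smaller. A change to the analysis section is worth making, but the documents do not show that harm would go undetected.

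**What to change.** In section 3 d):

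- For synechiae, and for infection as a secondary safety item, report the number of patients with the event on the treated side only, the untreated side only, both and neither. Give the paired risk difference with an unadjusted two-sided 95% confidence interval.
- Add a two-sided McNemar test as support, or a paired two-sided test of grades if the physician form is graded.
- State that the 30-test alpha does not apply to a finding of harm, and that a non-significant result is always reported with its upper confidence limit.
- Keep any claim that the agents reduce synechiae within the corrected family.

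In section 2 c), correct the conflict between 0.05/30 and 0.017 and state sidedness.

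The physician assessment weeks must be reconciled before the time point is fixed: section 2 c) gives 1 and 2 weeks after surgery, while section 3 b) f.) gives weeks 1, 3 and 6. The continuing-review entry under Expedited Paragraphs marks the remaining activities as limited to data analysis, so the change should be dated and labelled as made at that stage.

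The cost is wording only: the plan already has these outcomes recorded, so no extra patients or visits are needed. The downside is about a 5% false-alarm chance for each safety outcome, against 0.17% at 0.05/30.
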